Trauma Informed Guilt Reduction Therapy

NCT02512445

Original Document Date: November 14, 2024

8. Aims and Objectives

Primary Aim: To evaluate the efficacy of TrIGR for reducing deployment-related guilt in Veterans of OEF/OIF/OND.

Hypothesis 1: Veterans in TrIGR compared to Veterans in supportive care therapy (SCT), will have significantly greater reductions in deployment-related guilt severity at the end of treatment and post-treatment follow-up.

Secondary Aims: To examine whether TrIGR reduces distress and shame and improves quality of life. We are also interested in the degree to which gains are maintained during the follow up periods.

Hypothesis 2: Veterans in TrIGR, compared to Veterans in SCT, will have significantly greater reductions in distress, shame, guilt cognitions, avoidant coping, and significantly more improvement in their quality of life at the end of treatment and at post-treatment follow-up.

Hypothesis 3: Per the NAG model, guilt cognitions, distress and avoidant coping will partially mediate the treatment effect on guilt severity.

Exploratory Aim: By including Veterans with a variety of deployment-related presenting problems, we will be able to conduct exploratory analyses that will inform future research regarding for whom and under what conditions TrIGR is most effective.

Objective 1: To explore relationships between TrIGR effects and PTSD and depression symptom severity, suicidal ideation (SI) and alcohol/substance use.

Objective 2: To explore whether reductions in guilt, shame, and avoidant coping will partially mediate the treatment effect on PTSD symptoms among **Veterans with a PTSD diagnosis** and/or depression symptoms among **Veterans with a depressive disorder**.

9. Approach

9.1. Design. This prospective, randomized, controlled trial will assess the efficacy of TrIGR as compared to SCT for the treatment of male and female Veterans with guilt related to a traumatic event that occurred during deployment. 150 participants will be enrolled through the San Diego and Providence VAs and randomized at the individual level. All eligible participants will complete an in-person baseline assessment, receive 6 sessions of TrIGR or SCT in individual format, complete weekly measures related to the primary and secondary aims, and complete a follow-up assessment immediately post-treatment, and 3- and 6-months later.

9.2. Timeline. We propose a study lasting 4 years including:

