9.3. Procedures. Eligible Veterans will be recruited from two VA Medical Center sites, one in San Diego, CA, and one in Providence, RI. Potential participants will be receiving or presenting to care at VA enrollment, primary care, mental health, MST, or other VA services and will be referred by clinicians or staff in those clinics (see letters in Support 2e - 2g). Veterans may also self-refer to the study in response to advertising materials that will be distributed in patient areas and in the community. All potential participants will undergo a brief (15 minute) screen (following informed consent to be screened) conducted by the site project coordinator to determine preliminary eligibility. Veterans who meet the screening requirements will complete consenting procedures and will be invited for a full baseline assessment. Participants who meet inclusion/exclusion criteria as confirmed by the baseline assessment will be randomized to TrIGR or SCT. All participants will be assessed at baseline, immediately post-treatment, and at 3- and 6-month post-treatment follow-ups. Participants will be compensated for completing each of the four assessments with \$40 per assessment. We anticipate that baseline assessments will take approximately 3 hours and follow-ups will take approximately 2 hours. Participants will also complete brief weekly self-report assessments (15 minutes) during treatment. We will attempt to obtain follow-up data on all participants, regardless of whether they complete the intervention.

9.4. Participants: Inclusion/Exclusion Criteria, and Rationale. Participants will be male and female OEF/OIF/OND Veterans, at least 18 years of age, who endorse distress from guilt related to an event or events that occurred during a military deployment. Women and members of diverse ethnic and racial groups will be recruited for this project. Eligibility criteria were designed to recruit a heterogeneous and representative sample of Veterans with guilt and distress related to trauma that occurred on deployment. Eligibility criteria are broad in order to capture the many manifestations of distress related to guilt among Veterans.

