9.7.5. Standard Pharmacotherapy. In regard to pharmacotherapy, the VA follows treatment guidelines that require standardized prescribing practices for individuals with PTSD, depression, and AUD. We expect at least 85% of participants will be receiving medications based on these guidelines. We recognize that pharmacotherapy and changes in medications will be an uncontrolled source of variance but expect that any changes will be similar across treatment conditions and thus balanced by randomization. We considered recruiting participants who were not on medication or asking participants to be medication stable prior to study entry. However, psychotropic medications have well documented effectiveness for the treatment of PTSD, anxiety and depression and withholding such medication would be inappropriate for this high-risk population. Study coordinators will record from VA medical records and patient self-report all treatment (psychotherapy and medication) in which Veterans participate in the VA. Participants will also be asked about any treatment outside of the VA. We will compare treatment as usual between our two conditions and, if differences in any variables are found, include these as covariates in our analyses.

9.7.6. If Participants’ Alcohol/Substance Use Worsens During Treatment. If a therapist or assessor identifies worsening alcohol or substance use, the investigators will evaluate whether best clinical care indicates a need for more intensive SUD treatment. PIs will be contacted if a participant reports increased or risky substance use. If more intensive treatment is needed for any reason, we will assist in establishing treatment, then discontinue study participation following a final evaluation. Please see the Human Subjects section for the plan to address clinical worsening during study participation, including if participants display safety concerns such as suicidality or risk of violence.

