9.8. Research Assessments

9.8.1. Outcomes. The primary efficacy outcomes of interest are reduction in the severity of guilt related to a deployment trauma at post-treatment and follow-up. We will also examine distress, shame,

quality of life, PTSD symptoms, depression symptoms, alcohol and substance use, suicidality, and potential mediators and moderators including avoidant coping, guilt cognitions, treatment process variables (e.g., attendance, homework completion), gender, and cognitive performance. All measures can be found under Support Documents.

Primary Outcome. Trauma Related Guilt Inventory [TRGI; 18] is a 32-item validated self-report measure assessing traumatic guilt. The TRGI has three scales – Guilt Severity, Distress, and Guilt Cognitions. We will use the TRGI as one of our eligibility criteria (see inclusion criteria, section 9.4) and to monitor changes in guilt and related cognitions over time. Guilt severity will be the primary outcome of interest. It is computed by adding items regarding guilt frequency and guilt intensity. Changes in guilt cognitions will be examined as a partial mediator of treatment outcomes. Internal consistency is high for the TRGI (guilt severity = .90, distress = .86, guilt cognitions = .86).

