In the second stage, we will perform sensitivity analyses for the impact that potentially informative missing data may have on the analyses. The selected method of data analysis is robust with respect to drop-out and missing data, unless the drop-out mechanism or cause of missing is informative. We will use pattern-mixture models to assess if there is bias due to drop out or missing data. These mixed models allow us to assess whether important estimates are dependent on missing data patterns, and provide overall estimates of effects by averaging over the various missing-data patterns [80]. In addition, we will consider the extension of the Pattern-Mixture models [81], which includes the incorporation of random effects in the Pattern mixture model, which allow subject-to-subject heterogeneity. All hypothesis tests will be intent-to-treat, using SPSS version 21, and will be two-sided at the .05 level where applicable. We will adjust p-values for multiple testing within each hypothesis separately by using a Bonferroni correction whenever more than one variable is being tested.

Type I error will be controlled through the following steps. The data analysis method we selected reduces the number of dependent variables drastically. We have restricted potential predictors to those with strong evidence and/or strong rationale for having an effect on the dependent variable, and in most cases we have further restricted potential predictors to one representative of each. Also, an adjusted significance level (.01 rather than .05) will be used if applicable.

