Missing data values will be minimized by intensive training of the assessors in techniques of clarifying answers and checking questionnaires while participants are on-site. When missing values are identified, several approaches to acquire the necessary data will be employed: 1) if at all possible, participants will be rescheduled within 24 hours of completion of tests or interviews; 2) if a participant cannot be rescheduled, an effort will be made to send a tester to the individual's place of residence within the same period; 3) missing data will be examined to assess randomness. We expect missing data to be randomly distributed and will impute appropriate values (see below). Missing data (i.e., loss to follow up) will be tested to determine if it is informative, and the methods developed by [82] and [83] to test for completely random dropouts will be applied. If necessary, the techniques of [84] applicable to generalized

estimating equations models will be used to impute missing values.

We will test whether drop-out is random or systematic by comparing the drop-outs with the study completers on the baseline data. An absence of significant differences would support the random nature of drop-outs. Effect of drop-outs will be minimized by the following steps: First, selected data analysis method allows the inclusion of subjects who drop-out or were terminated early in the study, without relying on data imputation procedures. Therefore, no subjects will be excluded from the analyses due to their study status. Second, effect of any systematic differences between the drop-outs and completers will be explored by including the variable of concern to the model as a covariate.

9.11.2. Primary Outcome Analyses.

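### Section 9.7.6, read literally, ends study participation rather than study therapy when more intensive treatment is needed, and the supplied text does not reconcile this with the plan to follow everyone

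*Combined protocol and SAP*

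**What the plan says.** Section 9.7.6 covers worsening alcohol or substance use during treatment. The investigators judge whether more intensive care is needed. If it is, for whatever reason, "we will assist in establishing treatment, then discontinue study participation following a final evaluation". What ends is participation in the study, not only the study therapy. The same section continues: "Please see the Human Subjects section for the plan to address clinical worsening during study participation". That section is not among the supplied documents.

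Section 9.3 sets the general rule, with no exception: "We will attempt to obtain follow-up data on all participants, regardless of whether they complete the intervention". It schedules assessments at baseline, post-treatment, and 3 and 6 months after treatment.

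Section 9.8.1 makes the later scores part of the primary outcome: "The primary efficacy outcomes of interest are reduction in the severity of guilt related to a deployment trauma at post-treatment and follow-up".

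Sections 9.11.1 and 9.11.2 deal with missing scores:
- The mixed model "allows the inclusion of subjects who drop-out or were terminated early in the study, without relying on data imputation procedures". It uses every randomised participant with a baseline and at least one later evaluation.
- "Missing data (i.e., loss to follow up) will be tested to determine if it is informative", with imputation if necessary.
- "We will use pattern-mixture models to assess if there is bias due to drop out or missing data".
- Section 9.11.1 itself limits the model's claimed robustness to drop-out that is not informative.

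Section 9.1 adds that participants "complete weekly measures related to the primary and secondary aims". The supplied text does not say whether these include the guilt severity scale or enter the primary model. The contents of Table 3 (Measures) did not survive extraction.

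**The concern.** Two instructions to site staff point in different directions. Under 9.3, a participant who stops therapy early is still called for the 3- and 6-month visits. Under 9.7.6, a participant referred to more intensive care has one final evaluation and then leaves. The text does not say whether that evaluation replaces the post-treatment visit or whether later visits are cancelled.

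People who leave under 9.7.6 are selected by getting worse, so their missing follow-up scores may well be informative. That is the case in which section 9.11.1 says the model is not robust. Participants at risk of this exit are deliberately enrolled: section 9.4 admits mild and moderate alcohol and substance use disorders.

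If more TrIGR than SCT participants left this way, the TrIGR benefit at follow-up would be overstated. If more SCT participants left, it would be understated.

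**Working it through.** **The text.**
- Section 9.7.6 concerns the treatment period. Its action is to end study participation after one evaluation.
- Section 9.3 concerns everyone. Its action is to attempt follow-up whether or not the intervention is completed.
- Section 9.10.1 covers worsening in the follow-up phase. It provides referral and clinical monitoring and mentions no end to participation.
- Section 9.4 (*Who will not be excluded*) encourages ongoing substance-use treatment, so extra care does not by itself rule out being assessed.
- Sections 9.11.1 and 9.11.2 say how early leavers are analysed. They do not say whether visits continue.

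No supplied section ranks 9.3 and 9.7.6. The plan gives no figure on this point to reproduce.

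**Illustrative size.** Inputs from the documents: 75 per arm (150 in total); correlations of .2, .5 and .8 and a 0.5 SD effect (Power analysis); up to 20% attrition (9.5.4). Assumed, because the documents are silent:
- exit rates of 5% vs 2%, or 10% vs 5%, by arm;
- those who exit are s = 1 to 1.5 SD worse on guilt at 3 and 6 months, in both arms;
- a share f of that worsening already shows in k post-baseline scores taken before they leave;
- equal correlation ρ between all scores.

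The likelihood-based model predicts part of the lost worsening from the k scores. What remains is

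shift = (difference in exit rates) × s × m, with m = 1 − f·kρ/(1 + kρ).

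At ρ = .5:
- k = 1 (final evaluation only), f = .5: m = 1 − 0.25/1.5 = 0.833
- k = 4 (in-treatment guilt scores in the model), f = .5: m = 1 − 1/3 = 0.667
- k = 4, f = 1: m = 1 − 2/3 = 0.333

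| Case | 5% vs 2%, s = 1 to 1.5 | 10% vs 5%, s = 1 to 1.5 |
|---|---|---|
| k = 1, f = .5 | 0.025 to 0.038 SD | 0.042 to 0.063 SD |
| k = 4, f = .5 | 0.020 to 0.030 SD | 0.033 to 0.050 SD |
| k = 4, f = 1 | 0.010 to 0.015 SD | 0.017 to 0.025 SD |

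For example, 0.05 × 1.5 × 0.833 = 0.0625. Simulation with 2,000 trials per setting agreed: for k = 1, 0.025/0.039 at 5% vs 2% and 0.041/0.062 at 10% vs 5%. With equal 5% exits the shift was within 0.002 of zero.

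Standard error of the 6-month effect, adjusted for baseline: √(2/75 × 0.75) = 0.141 with no attrition, √(2/60 × 0.75) = 0.158 with 20%; about 0.15. The shifts are therefore 0.010/0.15 = 0.07 to 0.0625/0.15 = 0.42 standard errors. The error rate Φ(−1.96 + shift/SE) + Φ(−1.96 − shift/SE) of a two-sided 5% test becomes 5.1% to 7.0%.

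Other correlations change this moderately. For k = 1, f = .5, the largest shift is 0.05 × 1.5 × 0.917 = 0.069 SD at ρ = .2 and 0.05 × 1.5 × 0.778 = 0.058 SD at ρ = .8. At ρ = .8 the standard error also falls, to √(2/75 × 0.36) = 0.098, so that extreme is 0.60 standard errors and an error rate of 9.1%.

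**The case against.** **The missing section may settle it.** Section 9.7.6 sends the reader to a Human Subjects section that is not supplied. This stands. The claim is limited to the supplied text, and the fix allows for a cross-reference.

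**The two rules can be read together.** Section 9.3 only promises an attempt, and a specific clinical rule ordinarily overrides a general one. The authors may also have meant only that therapy stops. So a reader might infer a proven contradiction, and the documents do not support that: this is an ambiguity. But if the specific rule does govern, the follow-up scores are lost; if only therapy was meant to stop, the text should say so.

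**The group is probably small.** The rule covers a six-session treatment period, section 9.4 excludes severe use disorders, and section 9.10.1 handles later worsening without ending participation. This stands and limits the size.

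**The severity and exit rates are unsupported.** The trigger is mainly substance use, while the outcome is guilt. Those referred would then be receiving more care and might improve. This stands: the figures above are an illustration, not an estimate.

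**The analysis already has safeguards.** Besides those quoted, section 9.11.1 explores differences between drop-outs and completers as covariates, section 9.8.1 measures substance use repeatedly, and section 9.10.1 reviews drop-out rates. A reader might infer that these participants are dropped from the analysis or that intent-to-treat is broken. Neither follows: the model keeps them in their assigned arm with the scores they have. What the safeguards cannot do is supply scores that were never collected, or tell a coordinator whether to book the 3-month visit.

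**Conclusion.** The concern holds as an unreconciled rule on outcome collection, worth settling because it is cheap to settle. Its core is a matter of trial conduct; the analysis plan already covers early leavers.

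The likely bias is small, 0.01 to 0.06 SD in the main illustration at correlation .5, and zero if exit rates and severity match across arms. It needs two things that the documents do not show: more exits, or worse exits, in one arm, and markedly worse later guilt among those who exit.

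A reader might infer that the rule would favour TrIGR. Nothing in the documents says which arm would have more exits, so the direction is unknown. Nor is there a case here about power: these exits may already lie within the 20% attrition allowance. Confidence is medium, mainly because of the unseen Human Subjects section.

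**What to change.** Leave every referral and care decision as the investigators have set it. Amend section 9.7.6 so that only study therapy stops, for example: *Leaving study therapy does not end the scheduled post-treatment, 3-month and 6-month outcome assessments for participants who still consent.* Use matching wording in the Human Subjects section, or cross-refer to it if it already says this. Keep the final evaluation as an additional record, and report by arm how many participants left therapy under this rule.

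Cost: one sentence, plus visits already scheduled for every participant, at $40 and about 2 hours each (9.3). Exits occur during treatment, so up to three visits per person are added:
- 5% vs 2% exits: 75 × 0.07 = 5.25, about 5 participants; 5 × 3 = 15 visits, $600, 30 hours.
- 10% vs 5% exits: 75 × 0.15 = 11.25, about 11 participants; 11 × 3 = 33 visits, $1,320, 66 hours.

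If the final evaluation serves as the post-treatment assessment, two visits are added instead: 10 visits, $400 and 20 hours, or 22 visits, $880 and 44 hours. Some participants may decline or be unable to attend, so these are upper limits for the assumed exit rates.

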9.8. Research Assessments

9.8.1. Outcomes. The primary efficacy outcomes of interest are reduction in the severity of guilt related to a deployment trauma at post-treatment and follow-up. We will also examine distress, shame,

quality of life, PTSD symptoms, depression symptoms, alcohol and substance use, suicidality, and potential mediators and moderators including avoidant coping, guilt cognitions, treatment process variables (e.g., attendance, homework completion), gender, and cognitive performance. All measures can be found under Support Documents.

Primary Outcome. Trauma Related Guilt Inventory [TRGI; 18] is a 32-item validated self-report measure assessing traumatic guilt. The TRGI has three scales – Guilt Severity, Distress, and Guilt Cognitions. We will use the TRGI as one of our eligibility criteria (see inclusion criteria, section 9.4) and to monitor changes in guilt and related cognitions over time. Guilt severity will be the primary outcome of interest. It is computed by adding items regarding guilt frequency and guilt intensity. Changes in guilt cognitions will be examined as a partial mediator of treatment outcomes. Internal consistency is high for the TRGI (guilt severity = .90, distress = .86, guilt cognitions = .86).

Secondary Outcomes. The Brief Symptom Inventory-18 [BSI-18; 50] will be used for inclusion criteria and to assess change in self-reported distress over the study period. The 18 items are on a five-point Likert scale assessing the degree to which participants were distressed or bothered by mental health problems in the last seven days. The BSI-18 generates four scores: a total score [global severity index (GSI); scores ranging from 0 to 72], and three subscale scores for depression, somatization, and anxiety (scores ranging from 0 to 24). Internal consistency for the BSI is adequate ($\alpha = .89$ for GSI, $\alpha = .84$ for depression, $\alpha = .74$ for somatization, and $\alpha = .79$ for anxiety) and concurrent validity with the longer-form measure the BSI-18 was derived from ranges from .91 to .96. A Clinical Global Impressions Severity Scale [CGI-S; 51] rating of at least markedly ill will be required for study entry. The CGI-S requires clinicians to make two ratings on a 7-point categorical scale: (1) severity of illness within last seven days, and (2) global improvement from baseline. The CGI-S is commonly used in clinical trials to assess changes in distress severity, and has shown predictive utility in studies of schizophrenia, depression, social anxiety, and PTSD. We will use the CGI-S to assess clinician ratings of change in distress severity. In combination, the BSI-18 and the CGI-S will allow us to have multi-modal assessment (i.e. self-report and clinician rating) of distress severity.

We will measure shame using the Internalized Shame Scale [ISS; 66], a 30-item self-report measure assessing shame proneness scored on a 5-point Likert scale. The ISS yields sum scores for two subscales, self-esteem and internalized shame and has been well-validated with research and clinical populations. The World Health Organization Quality of Life [WHO-QOL-BREF; 89] is a 26-item measure that assesses quality of life across four domains: physical, psychological, social relationships, and environment. The WHO-QOL-BREF has excellent internal validity and test-retest reliability.

The Clinician-Administered PTSD Scale for DSM-5 [CAPS; 67] is a semi-structured interview used to assess PTSD diagnostic criteria and severity. Respondents select up to three of the most traumatic events they have experienced, and those events are used as the basis for assessing PTSD symptoms. The CAPS assesses each of the 20 items from the DSM-5 criteria B, C, D, and E and it has demonstrated high levels of internal consistency, good interrater reliability, and excellent convergent validity. The CAPS can be administered in about 60 minutes, and it has the advantages of categorical (diagnostic) or dimensional scoring of PTSD. The PTSD Checklist – 5 [PCL-5; 68] is a brief self-report instrument to measure PTSD symptom severity. It consists of 20 items, scored on a 5-point scale (0 = not at all to 5 = extremely), that correspond to the DSM-5 symptoms of PTSD. The PCL-5 is still being evaluated; however, preliminary studies report high internal consistency (alpha ranges between .95 and .97) and high correlations with the original PCL (between .88 and .97) [69].

Depression. The Patient Health Questionnaire [PHQ-9; 70] is a self-report scale listing common symptoms of depression. It is among the most widely used self-report depression measure in clinical populations, facilitating comparison between this investigation and others.

Exploratory outcomes. The Timeline Follow-back [TLFB; 71] will be employed at all assessment points to evaluate alcohol and other substance use during the 90 days preceding each interview. The Quantity-Frequency Index[72] and maximal consumption will be calculated for alcohol use. Drug use indices will be similarly derived for opiates, marijuana, and other drugs. The TLFB will be used at each follow-up to establish: percentage days heavy drinking, percent days abstinent, length of initial

abstinence, length of use episodes, severity of relapse and current alcohol/drug use pattern. A self-report Substance Use Inventory [SUI; 73] will be administered bi-weekly at treatment sessions. The inventory asked patients on which of the preceding seven days they had used alcohol or any of seven major types of drugs. Participants will be administered the AUD and SUD sections of the SCID for DSM-5 at baseline.

The Columbia-Suicide Severity Rating Scale [C-SSRS; 74] is a standardized 8 point clinician-administered rating system designed to track suicidal adverse events across a treatment trial and cover the wide spectrum of suicidality including ideation and intent.

The Brief COPE [75] is a 28-item measure of cognitive and behavioral coping scored on a Likert scale. It assesses coping styles including avoidant coping (e.g., denial, substance use, behavioral disengagement).

9.8.2. Baseline Measures. The Brief Neuropsychological (NP) Assessment Battery targets neurocognitive skills previously associated with substance abuse treatment outcomes [e.g., 53] and is limited in length (30 minutes) to facilitate compliance. All NP measures will be administered by the trained assessors in a standardized fashion designed to minimize fatigue and possible carryover effects (i.e., if a participant performed poorly on any one task). The measures, grouped by cognitive domain, include: 1) General Intelligence: American National Adult Reading Test (ANART); 2) Executive Functioning/Problem Solving: Wisconsin Card Sort; 3) Attention: WAIS-III Digit Symbol; 4) Verbal Learning and Memory: Hopkins Verbal Learning Test (HVLT). Each raw test score will be transformed into a T-score ($M = 50$, and $SD = 10$) based on the degree of deviation from the normative age-referenced mean score. Then, domain T-scores will be calculated for each subject by averaging T-scores within that domain. This brief battery takes approximately 30 minutes and is a shortened version of the assessment utilized in our previous studies.

Mental Health Problems. Modules of the Structured Clinical Interview for DSM-5 [SCID; 76] will be used to assess depressive disorders, alcohol and substance use disorders, and bipolar and psychotic disorders (for exclusion criteria). The research version of the SCID for DSM-5 will be available by the end of 2014 [77] (well in advance of when we would initiate this proposed study).

9.8.3. Treatment Process Measures. The Expectancy of Therapeutic Outcome (ETO), a 5-item self-report scale that evaluates treatment credibility, will be administered by the therapist in Session 1 after the therapist has provided the overall rationale for the treatment program. Questions are rated on a 0 to 8 Likert-type scale, with total scores from 0 to 32. The Additional Treatment Inventory (ATI) assesses additional treatment sought after the completion of study treatment. It asks about both psychiatric medications and psychotherapy. The Client Satisfaction Questionnaire [CSQ; 78] is an 8-item self-report scale measuring satisfaction with treatment. It has excellent internal consistency and correlates with therapists' estimates of client satisfaction. This instrument will be used to measure participants' satisfaction with the interventions.

Table 3. Measures

9.8.4. Medication Adherence. The ACTG Interview of Antiretroviral Medication Use (AIAM) will be used to assess medications that participants are taking and adherence to medication regimens. This interview was developed by the Adult AIDS Clinical Trials Group (ACTG) to assess in detail HIV medication adherence over the previous four days and takes about 10 minutes to complete [79]. The measure was modified for the current study to assess adherence for prescribed psychotropic medications by omitting references to HIV or AIDS and omitting the last item that lists side-effects that are common to HIV medications. The accuracy of self-reports of medication adherence has been questioned, and more objective methodologies are available, such as unannounced pill counts and medication bottle caps containing microchips that record medication adherence. However, for the current study, we have selected this self-report measure that requires less time, effort, and costs and has been validated when compared with other methods. Additionally, based on our prior research with Veterans, there are substantial differences in number and types of medications prescribed, complicating alternative non-self-report assessment procedures.

9.9.1. Assessor Training and Evaluation. Each site will have a primary assessor (15 hours per week) and a back-up assessor (up to five hours per week) who will be utilized if the primary assessor is unavailable or unblinded. Both will be blind to treatment condition. [name], [name], and [name] will train the assessors at both sites using audio-recordings recordings, role plays, and jointly conducted interviews and will hold weekly ongoing supervision. [name] will also view randomly selected audio-recordings of assessment sessions to provide feedback and ensure inter-rater reliability. During each assessment, the assessors will evaluate any major changes in health (e.g., overnight hospitalizations), possible adverse events, suicidal ideation, and general well-being. Therapists will also assess for clinically significant worsening during therapy sessions. Any exacerbation of symptoms or alcohol/substance use will be reported and discussed with [name] and the supervising investigator so that appropriate action can be taken if necessary. Data collection staff and intervention staff will be strictly separate. All assessors will complete standardized training to criterion for the CAPS, SCID, NP, and TLFB assessments. The assessor will observe a minimum of two assessments for each measure and then be observed for a minimum of two assessments. Additionally, the assessors will be tested for reliability (once every six months), and participate in weekly staff meetings to address questions. Training is also provided on common issues associated with self-report measures. These training procedures are all in place and have been on-going in [name], [name], [name], and [name] research labs.

9.9.2. Other Personnel. The San Diego site will have a full time coordinator who manages day-to-day operations and communication between the study sites and governing bodies. The Providence VA will have a half-time coordinator who manages the day-to-day operations of the Providence site. Each site will have two part time (10 hours/week) therapists (see section 9.7.3.) and two assessors, blind to treatment condition, who conduct study assessments (see section 9.9.1.).

9.10.1. Quality Control. Data Safety Monitoring will include periodic review and reporting of participant accrual, adverse event rates, treatment compliance, and drop-out rates. Study termination will be triggered by excessive drop-outs or adverse events. If treatment is needed during the follow-up phase due to increased substance use or serious psychiatric/medical symptoms, patients will be referred to appropriate treatment and followed by the PI and study psychiatrist until treatment is initiated. Adverse events will be reported to the DoD and VA IRBs and R&D (serious adverse events within 48 hours) and clinically managed as appropriate, including hospitalization if necessary. A summary of all adverse events will be submitted to the DoD annually. The PIs and a co-investigator (licensed psychologists in their respective states) will be available by pager 24-hours a day. The PI will be responsible for initial determination of serious adverse events from non-serious adverse events.

[name]. will serve as the medical monitor. Her functions include the following: (1) Review of research protocol and plans for data safety and monitoring; (2) Evaluation of the progress of the study every 6 months, including the quality of data collection, security and quality, participant recruitment/retention, participant risk and benefit, and any other factors affecting study outcome; (3) Consultation regarding continuation or termination or other modifications of the trial in the service of protecting safety of study participants; and (4) Evaluation of study adverse events and consultation to maximize protection of participants. Progress evaluations every 6 months will be provided to VA IRB, R&D, and HRPO, and study investigators. The medical monitor is not an investigator in the study and does not have any conflict of interest.

9.10.2. Data entry and management. All data are collected on forms, which are identified by a unique participant ID number, protocol ID number, and protocol phase and visit, and are entered into already exiting Microsoft Access[©] database. A protocol data collection schedule is used to monitor participant progress through the protocol, missing assessments, and other protocol deviations during the study. Participants will be queried immediately to complete or clarify blank or illegible responses. Refusal or inability to respond to items will be coded, with explanations documented. Data entry screens incorporate range checks or lists of valid responses for each item. Forms with missing or invalid data in key identifying fields are referred back to raters for correction before entry. Other missing or invalid data will not prevent the form from being entered, but will be flagged for correction. Participant confidentiality

is maintained by methods described in the Human Subjects protocol by keeping identifying information separate from study data in secure location and restricting study data access to specified personnel. Only approved study personnel will have access to study data, and all study personnel will be trained regarding privacy and security issues. Most authorized personnel will have read-only access to digital data; write/edit access will be restricted to study data management staff. Data management and statistical analysis will be performed/supervised by the study statistician, [name].

Secure information will be accessed, stored, and destroyed according to a data security plan that will promote security and privacy. Data entry and security procedures have been in place in Drs. [name], [name], [name], [name], and [name]'s studies over the course of many trials.

9.11. Statistical Considerations.

9.11.1. Statistical Analyses. In the initial 3-6 months, data management procedures will be developed and put into practice. Data will be entered as it is collected and quality assurance checks conducted on an on-going basis (e.g., double entry and cross validation). Data analysis will be performed in multiple stages. In the initial stage, analyses will be conducted on an on-going basis to assure strict adherence to important issues for clinical trials, such as treatment fidelity, therapeutic alliance, and therapist effects. Next, preliminary analyses will be performed by examination of the distribution of variables to assess their characteristics (means, standard deviations, and skewness). Descriptive statistics and graphs will be used to summarize the characteristics of the study population. Continuous measures will be tested for normality and homogeneity of variance. Non-normally distributed variables will be transformed to meet the normal distribution assumption for linear models. Randomization will be assessed by performing a series of Wilcoxon-rank sum tests, ² or Fisher's exact tests to compare the groups on demographic and initial baseline clinical variables. Any variables on which the groups differ initially will be explored as covariates in subsequent analyses, as described in detail for each hypothesis, and we will take this into account in the interpretation of the outcome.

In the second stage, we will perform sensitivity analyses for the impact that potentially informative missing data may have on the analyses. The selected method of data analysis is robust with respect to drop-out and missing data, unless the drop-out mechanism or cause of missing is informative. We will use pattern-mixture models to assess if there is bias due to drop out or missing data. These mixed models allow us to assess whether important estimates are dependent on missing data patterns, and provide overall estimates of effects by averaging over the various missing-data patterns [80]. In addition, we will consider the extension of the Pattern-Mixture models [81], which includes the incorporation of random effects in the Pattern mixture model, which allow subject-to-subject heterogeneity. All hypothesis tests will be intent-to-treat, using SPSS version 21, and will be two-sided at the .05 level where applicable. We will adjust p-values for multiple testing within each hypothesis separately by using a Bonferroni correction whenever more than one variable is being tested.

Type I error will be controlled through the following steps. The data analysis method we selected reduces the number of dependent variables drastically. We have restricted potential predictors to those with strong evidence and/or strong rationale for having an effect on the dependent variable, and in most cases we have further restricted potential predictors to one representative of each. Also, an adjusted significance level (.01 rather than .05) will be used if applicable.

